5.3.2. Analysis Methods

Descriptive statistics

The descriptive statistics that will be shown may include the number of subjects, mean, standard deviation, standard error, 95% CI, median, range, interquartile range, and geometric mean with corresponding 95% CI.

Kaplan-Meier analysis, Gehan-Wilcoxon test and Log-rank test

All Time-to event variables will be analyzed using a stratified Gehan-Wilcoxon test, a stratified log-rank test and Kaplan-Meier estimates. A summary table including number of subjects included in the analysis, number of subjects censored, 25th and 75th percentiles and median time-to event, with 95% confidence intervals based on log-log transformation method, and the p-values calculated based on the stratified Gehan-Wilcoxon test and stratified log-rank test will be presented.

The data will be presented graphically using the Kaplan-Meier estimate of the survival function by treatment.

For subgroup analyses, Kaplan-Meier plots will be produced per subgroup and Gehan-Wilcoxon test will be produced for each category of a subgroup.

Accelerated failure time (AFT) model

When indicated, time-to event variables will be compared between pimodivir and placebo using an accelerated failure time (AFT) model. The distribution to be used will be determined based on the goodness of fit of the model using Akaike's information criterion and will be selected from the following parametric families: lognormal, log-logistic, or Weibull. The AFT model will include the fixed categorical effects for treatment (with placebo as the reference) and stratification factors. The scale parameter will be the same across groups.

A summary of the final AFT model will include parameter estimates and associated standard errors, estimated accelerated failure time ratios versus placebo and associated 95% confidence intervals, and p-values. The survival curves per treatment group of the accelerated failure time model will also be shown with the Kaplan-Meier plots included in the same output.

For subgroup analyses the survival curves will be shown for each subgroup category separately.

Bootstrapping with replacement, and also considering the actual proportion of subjects in each stratum, will be used to obtain a 100% sample size 10001 times. The median (95% CI) time-to event will be derived from the 10001 bootstrapped samples.

Cox Proportional Hazard model

A stratified Cox proportional hazards model will be used adjusted for the stratification factors. The hazard ratio for the comparison of pimodivir versus placebo will be reported together with the 95% confidence interval. A Log-log plot of survival will be added to check the proportional hazard assumption of the Cox proportional hazards model.

For subgroup analyses the Log-log plot of survival will be shown for each subgroup category separately.

Logistic regression model

A logistic regression model (applying Firth's penalized likelihood approach) with treatment group and stratification factors as fixed effects, will be used to analyze the binary outcome and to obtain the odds ratios (95% CI) for the comparison of pimodivir versus placebo.

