#### Secondary Endpoint

The secondary endpoints are:

- Safety and tolerability based on assessment of AEs, clinical laboratory assessments, 12-lead ECGs and vital signs.
- The hospital admission rate 28 days after treatment initiation.
- Incidence of complications associated with influenza after the start of study treatment:
  - Pulmonary complications:

The pulmonary complications of influenza include respiratory failure, primary viral pneumonia, secondary bacterial pneumonia (including pneumonia attributable to unusual pathogens), exacerbations of chronic underlying pulmonary diseases such as COPD, asthma, and bronchitis.

- Respiratory failure: defined as either hypoxemic respiratory failure characterized by an arterial oxygen tension (PaO2) lower than 60 mmHg with a normal or low arterial carbon dioxide tension (PaCO2), or hypercapnic respiratory failure characterized by a PaCO2 higher than 50 mmHg.
- Primary viral pneumonia: a progressive event involving the lower respiratory tract with bilateral and/or diffuse radiological findings. No bacterial agent is identified using sputum cultures.
- Secondary bacterial pneumonia (including pneumonia attributable to unusual pathogens): a clinical event compatible with lower respiratory tract involvement, with lobar infiltrates on radiological studies and/or microbiological isolate of a bacterial pathogen, including unusual pathogens.
- Exacerbations of chronic underlying pulmonary diseases such as COPD and asthma: subjects with documented medical history of COPD or asthma with a sudden worsening of symptoms and deteriorating respiratory function (the latter as evidenced by worsening hypoxia, tachypnea, etc.) The event must start before a full recovery from the influenza infection occurred.
- Bronchitis

- Extrapulmonary complications:
  - Cardiovascular and cerebrovascular disease (eg, myocardial infarction, congestive heart failure, arrhythmia, stroke)
  - Muscular disorders (eg, myositis, rhabdomyolysis)
  - Central nervous system (CNS) involvement
  - Acute exacerbation of chronic kidney disease
  - Severe dehydration
  - Decompensation of previously controlled diabetes mellitus
  - Other infections (eg, sinusitis, otitis)

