9. A woman must agree not to donate eggs (ova, oocytes) for the purposes of assisted reproduction during the study and for a period of at least 30 days after the last dose of study drug.
10. During the study and for a minimum of 1 spermatogenesis cycle (defined as approximately 90 days) after receiving the last dose of study drug, in addition to the highly effective method of contraception being used by the female partner, a man regardless of having been vasectomized
  - Who is sexually active with a woman of childbearing potential must agree to use a barrier method of contraception (eg, condom preferably with spermicidal foam/gel/film/cream/suppository).
  - Who is sexually active with a woman who is pregnant must use a condom.
  - Must agree not to donate sperm.

Note: If the female sexual partner is postmenopausal (defined as no menses for 12 months without an alternative medical cause), is permanently sterilized (eg, hysterectomy, bilateral salpingectomy, bilateral oophorectomy), or otherwise incapable of becoming pregnant, the birth control methods mentioned are not applicable.

11. Willing and able to adhere to the prohibitions and restrictions specified in this protocol (see Section 4.3).
12. Subjects 13 to 65 years of age, inclusive must also have at least one of the following:

- a. Cardiovascular or cerebrovascular disease (including congenital heart disease, chronic heart failure, coronary artery disease, or stroke; excluding isolated hypertension).
- b. Chronic lung disease (eg, asthma, chronic obstructive lung disease [COPD] or cystic fibrosis).
- c. Weakened immune system due to disease or medication (eg, subjects with human immunodeficiency virus [HIV], cancer, or chronic liver or kidney disease [presence of kidney damage for >3 months, defined by structural or functional abnormalities of the kidney, with or without decreased GFR manifested by: pathological abnormalities; OR markers of kidney damage, including abnormalities in the composition of the blood or urine or abnormalities in imaging tests], or subjects taking chronic systemic steroids).

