### ***Secondary Endpoints***

The incidence of hospital admissions 28 days after treatment initiation will be analyzed using a logistic regression. Stratification factors will be added as covariates to the model.

Return to daily activities will be assessed once daily by means of the question 'Over the past 24 hours, how much has influenza (flu) interfered with your ability to carry out your daily activities?' The responses will be dichotomized: 'Not at all' and 'A little bit' will be considered as returned to daily activities and 'Somewhat', 'Quite a Bit' and 'Very much' will be considered as not having returned to daily activities. "Time to return to daily activities" is defined as the time from initiation of study treatment to when return to daily activities is reached for at least 24 hours. This endpoint will be analyzed analogously to the primary endpoint.

Time to resolution of fever will be analyzed analogously to the primary endpoint.

The incidence of treatment-emergent adjudicated complications will be analyzed using a logistic regression. Stratification factors will be added as covariates to the model.

The time to viral negativity, by qRT-PCR and viral culture, will be analyzed analogously to the primary endpoint. The viral load over time will be analyzed using mixed effects modeling. Stratification factors will be added as covariates to the model. Additional predictive baseline covariates may be added.

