1.2. Trial Design

This is a Phase 3, randomized, double-blind, placebo-controlled, multicenter study to evaluate the efficacy and safety of pimodivir in combination with SOC treatment versus placebo in combination with SOC treatment in adolescent (13 to 17 years), adult (18 to 65 years), and elderly (>65 to ≤85 years) non-hospitalized subjects with influenza A infection who are at risk of developing complications. A target of 720 subjects will be randomly assigned in this study with 360 subjects planned per treatment arm. The aim is to enroll a minimum of 72 adolescent subjects in this study in selected countries and study sites consistent with local regulations. The target population of the study are influenza-infected, non-hospitalized subjects who, due to their age (65 to 85 years) or underlying comorbidities (regardless of age), are at increased risk of developing influenza-related complications. The randomization will be stratified by type of baseline SOC (including or not including antiviral treatment) and time since onset of symptoms (first administration of study drug ≤48 hours or >48 hours since onset of influenza symptoms). The study population should consist of at least 60% of subjects with first administration of study drug ≤48 hours since onset of influenza symptoms.

Subjects who meet all eligibility criteria will be randomized in a 1:1 ratio to receive 1 of the following 2 treatments:

- Treatment Arm 1: pimodivir 600 mg bid for 5 days + SOC treatment*
- Treatment Arm 2: pimodivir placebo bid for 5 days + SOC treatment*

* SOC treatment will be determined by the investigator based on local practice, and may include influenza antivirals and/or supportive care only. The choice to use influenza antivirals as part of the SOC should be made before randomization. The influenza antiviral should be started no later than Day 2 morning (up to noon). An influenza antiviral as part of the SOC cannot be changed (eg, switching one influenza antiviral for another) during the treatment period, with the exception that an influenza antiviral may be discontinued in the case of a suspected adverse event (AE).

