5.1. Analysis Specifications

5.1.1. Level of Significance

As a confirmatory strategy, to account for multiplicity in the statistical evaluation of the most important efficacy endpoints, hierarchical testing will be applied to control for overall Type I error. The following endpoints are included in the confirmatory strategy:

Primary Endpoint

- Time to resolution of the 7 primary influenza-related symptoms (cough, sore throat, headache, nasal congestion, feeling feverish, body aches and pains, fatigue)

Secondary Endpoints

- Incidence of complications associated with influenza after the start of study treatment
- Hospital admission rates 28 days after treatment initiation

First, the primary endpoint will be tested for superiority of pimodivir in combination with SOC over placebo in combination with SOC at the 2-sided 5% significance level. If superiority is shown on the primary endpoint, the first secondary endpoint in the sequence as indicated above will be tested for superiority at the same significance level. If superiority is shown for this secondary endpoint, the second (and last) secondary endpoint in sequence will be tested. In case superiority is not shown for an endpoint, no further endpoints in the sequence will be tested for superiority.

This testing procedure will be applied on the ITT-i set.

The final analysis on the ITT-i set (to support FDA marketing authorization approval) and the final analysis on the OST subset (to support marketing authorization approval in EMA) will be performed independently, using a 5% two-sided significance level for each.

Statistical Methodology for Evaluation at the Final Analysis

The p-values for the final analysis of the primary endpoint and the two most important secondary endpoints will be based on an inverse-normal combination test. For the primary endpoint, the p-values are obtained from the Gehan-Wilcoxon test. For incidence of complications associated with influenza after the start of study treatment and Hospital admission rates 28 days after treatment initiation the p-values will be obtained from a logistic regression model (see Sections 5.3.2 and 5.3.2.2).

All p-values below are one-sided p-values, to evaluate rejection of the null hypothesis that pimodivir is not better than placebo.

Let:

- p = p-value from the analysis of the ‘pre interim’ category of the ‘study period’ subgroup
- q = p-value from the analysis of the ‘post interim’ category of the ‘study period’ subgroup

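### The confirmatory logistic models for complications and hospital admission leave out baseline chronic lung disease: a modest loss of efficiency, cheap to recover, and not a validity error

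*SAP*

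**What the plan says.** - **Model.** SAP 5.3.2 defines a Firth-penalized logistic regression "with treatment group and stratification factors as fixed effects, will be used to analyze the binary outcome". Protocol 11.4 names the same covariates for both binary endpoints.
- **Role.** These endpoints are tests 2 and 3 of the hierarchy, each "at the 2-sided 5% significance level". For both, SAP 5.1.1 states that "the p-values will be obtained from a logistic regression model", fitted separately to subjects enrolled before and after the interim and then joined by the inverse-normal combination.
- **Covariates.** Randomization is "stratified by type of baseline SOC (including or not including antiviral treatment) and time since onset of symptoms". Protocol 3.2 justifies the first factor as predicting time to symptom recovery and the second by its effect on antiviral efficacy. It does not mention complications or admission.
- **Oseltamivir subset.** SAP 5.1.1 tests this subset independently at 5%. SAP 5 drops SOC type there, leaving time since onset as the only covariate.
- **Lung disease.** Protocol 2.1.2 restricts the exacerbation component to "subjects with documented medical history of COPD or asthma with a sudden worsening of symptoms and deteriorating respiratory function". Inclusion criterion 12, which lists chronic lung disease under 12b, opens with "Subjects 13 to 65 years of age, inclusive must also have at least one of the following". Medical history is collected from all subjects at screening (Time and Events Schedule; Protocol 9.1.2). Chronic lung disease is neither a covariate nor a subgroup in SAP Table 6.
- **Age.** Age group is a Table 6 subgroup, with a treatment-interaction model for both binary endpoints (SAP 2.3).

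**The concern.** Where the plan models other outcomes, it adds a baseline variable suited to that outcome: the symptom score in the AFT and Cox models for symptom resolution, and viral load or titer in the viral models. The binary models have no counterpart. Protocol 11.4 does allow extra predictive covariates, but that sentence follows the viral-load model.

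A subject without prior COPD or asthma cannot contribute to the exacerbation component, so for complications the link with lung disease is partly built into the definition. For hospital admission the link is only the general one in SAP 1.2, that subjects with "underlying comorbidities (regardless of age), are at increased risk of developing influenza-related complications".

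Omitting a prognostic covariate from a logistic model moves the treatment odds ratio toward 1 and costs some power. Protocol 11.3 sizes the trial on the primary endpoint alone, so tests 2 and 3 have no stated power to draw on.

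**Working it through.** **1. The plan's own figure.** There is none for these endpoints. The 90% in Protocol 11.3 is for the Gehan-Wilcoxon test of the primary endpoint and does not bear on this point.

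**2. Inputs from the documents.**
- Evaluable subjects: 720 × 0.85 = 612, or 306 per arm.
- Interim at 540 enrolled, the upper end of the planned window: stages of 540 × 0.85 = 459 and 180 × 0.85 = 153. Weights are √(540/720) = 0.866 and √(180/720) = 0.5.
- The only complication rates given are 7.9% and 15.6%, from the hospitalized Phase 2 study (Protocol 1.1), which is a different population. They imply an odds ratio of (0.079/0.921)/(0.156/0.844) = 0.464.

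**3. Assumptions, none from the documents.** Lung disease 45%, independent of age; ages 13-17/18-65/66-85 in proportions 10/55/35%; antiviral SOC 60%; onset over 48 hours 40%; neither stratification factor prognostic; control rates of 5% and 10%.

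**4. Rough unadjusted power at 306 per arm.** 84% (15.6 vs 7.9%), 65% (10 vs 5%), 37% (5 vs 2.5%).

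**5. Models compared, Firth-penalized, Wald test, one-sided 0.025.**
- Current: logit P = b0 + b1·treatment + b2·SOC + b3·onset
- Plus lung: the same + b4·lung disease
- Plus lung and age: the same + two age-group terms
- Two-stage test: C = 0.866·Φ⁻¹(1−p) + 0.5·Φ⁻¹(1−q); reject if C > 1.96.

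**6. Two-stage power (%), treatment odds ratio 0.5, age given no effect, 2,500 runs per row.**

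| Control rate | Lung OR | Current | Plus lung | Gain | Plus lung and age |
|---|---|---|---|---|---|
| 10% | 3 | 55.8 | 58.2 | 2.4 | 58.7 |
| 10% | 5 | 54.0 | 55.7 | 1.7 | 55.9 |
| 5% | 3 | 30.5 | 31.2 | 0.7 | 32.6 |
| 5% | 5 | 29.8 | 31.1 | 1.3 | 32.7 |

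Monte Carlo error is about √(0.55·0.45/2500) = 1 point per figure. A separate two-stage run with lung odds ratios of 2 to 5 gave gains of 0.5 to 2.3 points from lung disease alone, with one-sided size of 2.2 to 2.5%.

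**7. Weaker predictors, single stage, N = 612, control rate 10%, treatment odds ratio 0.5, 3,000 runs.**

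| Lung OR, age OR | Current | Plus age | Plus lung |
|---|---|---|---|
| 1.5, 1 | 58.7 | 59.0 | 58.3 |
| 2, 1.5 | 58.9 | 59.3 | 59.5 |
| 3, 1.5 | 58.5 | 58.6 | 59.4 |

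Error is near 0.9 point per figure. At a lung odds ratio of 1.5 no gain is visible. Age alone adds at most 0.4.

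**8. Both variables prognostic and both added, single stage, 6,000 runs.** With odds ratios from 1.5 each up to 5 (lung) and 3 (age):
- 15.6% control rate, treatment odds ratio 0.464: from 83.1→83.5% up to 77.7→81.2%.
- 10%, odds ratio 0.5: from 58.5→58.8% up to 53.7→56.7%.
- 5%, odds ratio 0.5: from 32.7→34.4% up to 31.5→34.1%.

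Gains run from 0.3 to 3.5 points. Under the null in this set, including a two-stage run, one-sided size was 1.8 to 2.4% with or without the covariates.

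**9. Attenuation.** A conditional odds ratio of 0.464 is estimated by the current model as 0.468, 0.475, 0.488 and 0.499 as the covariates strengthen. The adjusted model gives 0.465 to 0.466.

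**The case against.** **The current model is complete and valid.** It is pre-specified, protocol and SAP agree on its covariates, and its size is controlled. The shift toward 1 is non-collapsibility: the model targets a less conditional odds ratio. All of this stands, so a reader who inferred a biased test or inflated type I error would be wrong.

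**Lung disease need not be a strong predictor.** Exacerbation is one of twelve complication categories in Protocol 2.1.2, and most of the others do not depend on lung disease. Subjects aged 65 or younger without lung disease must have another qualifying condition, so they are at risk too. This stands: the precondition shows a link but not its strength. A reader might posit sharp contrasts. With half the subjects having lung disease, placebo risks of 30% vs 3% and a treatment odds ratio of 0.55, power rises from 60.6 to 65.3%. Those risks imply a lung odds ratio of (0.30/0.70)/(0.03/0.97) = 13.9, and nothing in the documents supports so large a value.

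**Criterion 12b does not cover everyone.** Subjects over 65 qualify by age, so it would be wrong to infer that lung disease is established for every subject as part of eligibility. The data exist in the screening history, but SAP 4.7 only tabulates or lists that history. A definition is needed.

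**Age.** A reader might want age group added on the same argument. Every younger subject must have a comorbidity and older subjects need not, so even the direction of the age effect is unclear. Age also has its own interaction model.

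**Sparse events and timing.** At control rates of 5 to 10%, 153 second-stage subjects yield about 6 to 12 events. The simulations show no harm from one added term: size with lung disease alone was 2.2 to 2.5%. On timing, SAP Amendment 3 (1 July 2020) postdates the interim cut-off of 28 February 2020, so a change would follow an unblinded IDMC review. SAP 3.1 confines unblinding to the IDMC and its support group, so blinded staff can still make it.

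**Conclusion.** The point holds as an efficiency recommendation for chronic lung disease. The models behind tests 2 and 3 use covariates chosen for other outcomes and omit a variable that is already collected and tied by definition to one component of the complications endpoint.

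For lung-disease odds ratios of 2 to 5, the recoverable power is roughly 0.5 to 3 points. That is small beside the baseline power of about 30% and 55% for the two-stage test at control rates of 5% and 10%. The size depends on assumed event rates, prevalence and odds ratios. The existence of a gain depends on lung disease being a real predictor in this population, which the documents support only qualitatively.

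The documents do not support reading this as a defect in the confirmatory test, as a large loss of power, or as an equal case for age group.

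**What to change.** 1. Define baseline chronic lung disease (yes/no) from the screening medical history for every subject, with a fixed term list and including those over 65. SAP Attachment 1 already relies on documented prior asthma or COPD to classify anticipated events, so part of this derivation is needed anyway.
2. Add it as a fixed effect to the Firth models for complications and hospital admission, in both stages of the combination test and in the oseltamivir-subset analysis.
3. Align Protocol 11.4 and the matching synopsis text with SAP 5.3.2.
4. Have blinded staff make and date the change before unblinding.
5. Keep the current model as a sensitivity analysis.
6. Treat age group as optional.

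**Cost:** no new data, but a protocol change as well as SAP wording. There is one more parameter in a second stage that may hold few events, and the odds ratio becomes conditional on one more factor.

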5.3.2.1. Symptoms of Influenza (Flu-iiQ™ Module 1)

Composite symptoms scores (systemic symptoms, respiratory symptoms)

The actual composite symptom scores and changes from baseline will be shown descriptively and by mean (SE) plots per analysis visit and timepoint.

Time to resolution of: cough; sore throat; headache; nasal congestion; feeling feverish; body aches and pains; fatigue; neck pain; interrupted sleep; loss of appetite; the 7 primary influenza-related symptoms considering improvement from baseline

The time to resolution of cough, sore throat, headache, nasal congestion, feeling feverish, body aches and pains, fatigue, neck pain, interrupted sleep, loss of appetite, and the 7 primary influenza-related symptoms, improvement from baseline will be analyzed by Kaplan-Meier analysis, Gehan-Wilcoxon test, log-rank test, AFT model, and Cox proportional hazards model.

The AFT and Cox models will include the fixed categorical effects for treatment (with placebo as the reference) and stratification factors and the baseline symptom score as a continuous variable.

If the baseline symptom score is missing, then the baseline score will be imputed as the median score from all subjects in the ITT-i set.

